7. STUDY POPULATION

7.1 Subject Disposition

Subject disposition will be summarized for all subjects. Summaries will include: the number of subjects screened, the number of enrolled subjects, the number of subjects in each analysis population, the number of subjects completing or withdrawing from the study, and the primary reason for discontinuation.

7.2 Protocol Deviations

Major protocol deviations will be summarized by deviation category and treatment group. All protocol deviations will be listed.

7.3 Demographic and Baseline Characteristics

Demographic variables include: age, sex, ethnicity, and race. Age will be calculated in years relative to the informed consent date. Other baseline characteristics include: medical history, baseline melanoma disease characteristics, selected previous melanoma treatment, height, weight, body mass index (BMI), etc. Descriptive statistics will be presented for demographic and baseline characteristics for the Safety Population.

7.4 Concomitant Medications

Concomitant medication verbatim terms on electric case report forms (eCRFs) will be mapped to Anatomical/Therapeutic/Chemical (ATC) class and Preferred Names using the World Health Organization (WHO) Drug Dictionary Enhanced (version March 1, 2015).

Concomitant medications will be summarized for each dose group as well as for all subjects in each treatment arm by WHO ATC class and preferred name. These summaries will present the number and percentage of subjects using each medication. Subjects may have more than one medication per ATC class and preferred name. At each level of subject summarization, a subject is counted once if he reported one or more medications at that level. Each summary will be ordered by descending order of incidence of ATC class and preferred name within each ATC class.

Any concomitant medications identified as sensitive and narrow therapeutic range CYP substrates will be listed including any adverse event(s) that started during the duration of the IMO-2125 treatment. The medications of interest are as follows:

Drug Category	Preferred Term
Sensitive CYP3A4 substrates	budesonide, buspirone, eplerenone, eletriptan, felodipine, fluticasone, lovastatin, midazolam, saquinavir, sildenafil, simvastatin, triazolam, vardenafil
CYP3A4 substrates with a narrow therapeutic range	alfentanil, astemizole(a), cisapride(a), cyclosporine, diergotamine, ergotamine, fentanyl, pimozide, quinidine, sirolimus, tacrolimus, terfenadine(a)
Sensitive CYP1A2 substrates	Alosetron, duloxetine
CYP1A2 substrates with a narrow therapeutic range	theophylline, tizanidine
Sensitive CYP2C8 substrates	repaglinide
CYP2C8 substrates with a narrow therapeutic range	paclitaxel
CYP2C9 substrates with a narrow therapeutic range	phenytoin , warfarin
Sensitive CYP2C19 substrates	omeprazole
CYP2C19 substrates with a narrow therapeutic range	s-mephentytoin
Sensitive CYP2D6 substrates	desipramine
CYP2D6 substrates with a narrow therapeutic range	thioridazine

8. EFFICACY ANALYSES

The primary analysis of efficacy in the Phase 2 IMO-2125 + ipilimumab arm, including the hypothesis test of the ORR, will be performed on the first 21 patients in the PIIIE Population as defined in Section 6. An analysis of those in the SIIIE Population will also be performed; efficacy analysis in the combined PIIIE and SIIIE Population may also be summarized. The primary analysis of efficacy in the Phase 2 IMO-2125 + pembrolizumab arm will be performed on the PPIIE Population as defined in Section 6.

Patients will be categorized into subgroups based on whether they had previously been treated with talimogene or another oncolytic viral vector prior to enrollment in this study for some analyses.

8.1 Best Overall Response

The best overall response is the best response across all disease assessment visits after baseline taking into account requirements for confirmation. For any response criteria, the best overall response for each subject will be determined by examining investigator-assessed visit-level responses and determining the best confirmed response using the assignment rules in Section 8.1.1 or Section 8.1.2, as appropriate (Paules et al, 2010). Only visit-level disease assessments prior to the start of new anti-cancer therapy or response per the appropriate criteria will be considered.

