8.1.1 Confirmed Response using RECIST v1.1

Table 6 shows how the investigator-assessed Best Overall Confirmed Response is assigned for each subject. The table is based on the Best Overall Response confirmation table in the RECIST v1.1 guidelines (Appendix C).

Table 6: Confirmed Response using RECIST V1.1

Visit-Level Response	Next Visit Level Response	Confirmed Response
CR	CR	CR (if visit-level disease assessments are \geq 28 days apart), otherwise SD
CR	PR	PR (if visit-level disease assessments are \geq 28 days apart); otherwise SD
CR	SD	SD
CR, PR, SD	PD	SD
CR, PR	NE	SD
PR	CR, PR	PR (if visit-level disease assessments are \geq 28 days apart); otherwise, SD
PR	SD	SD
SD	SD, CR, PR, PD, NE	SD
PD	PD	PD
NE	NE	NE
CR, PR, SD	No 2 nd visit	SD
PD	No 2 nd visit	PD
NE	No 2 nd visit	NE

CR = complete response, PR = partial response, SD = stable disease, PD = progressive disease,
NE = not evaluable.

The minimum interval for confirmation of CR and PR is 28 days. Subjects must have at least one post-baseline disease assessment to be assigned SD as the best overall response; otherwise, there is no minimum interval for assignment of SD as the best overall response. Because scans of target and non-target lesions can be done on different dates, time between disease assessments is determined using the following algorithm: (1) calculate the time in days between initial and confirmatory scans for all target and non-target lesions separately (confirmatory assessment date - initial assessment date +1); (2) select the minimum time; and (3) compare to 28 days to determine if the confirmation criterion were met. Date of confirmed best overall response is determined using scan dates as follows: if BOR is CR or PR response date is the latest date of target or non-target lesion scan date or else use the assessment date.

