8.5 Efficacy Endpoints

ORR is defined as the proportion subjects with a best confirmed overall response of complete response (CR) or partial response (PR), with assessment of response to be determined by the investigator using irRECIST and RECIST v1.1.

OS is defined as the number of months from initiation of treatment to death from any cause. Subjects who have not died at their last contact will be censored on the date of last contact. The specifications for the time to death calculation are:

- If death is reported either on AE or Death CRF pages, OS will be calculated as *Date of Documentation of (Death – First Dose Date + 1) / 30.4375*.
- Subjects will be censored at their last contact date if death is not reported at the data cut-off date for study closure, and their survival time will be calculated as *(/Last Contact Date - First Dose Date + 1) / 30.4375*). Last contact date is defined as the last date reported among, Adverse Event (AE start date), the Study Exit Status, Hematology, Chemistry, Assessment of RECIST v1.1 Response, Assessment of irRECIST Response, Long Term Follow Up, Study Drug Administration (IMO-2125), ipilimumab Infusion and pembrolizumab Infusion pages of the eCRF.
- Subjects lacking data after the date of first dose who do not die will have their survival time censored on the date of first dose with duration of 1 day.

PFS, defined as number of months from the initiation of treatment to disease progression using RECIST v1.1 or irRECIST or death from any cause, will be calculated as *([Date of Documentation of Death or Disease Progression – First Dose Date + 1]/30.43750*. Subjects without reported progression at their last contact date will be censored on the date of their last valid disease assessment. A valid disease assessment is any disease assessment with overall visit-level response of irCR irPR, irSD, or irPD (without subsequent confirmation) when using irRECIST and CR, PR, or SD when using RECIST v1.1. Subjects who start new anti-cancer therapy before a PFS event will be censored on the date of initiation of new anti-cancer therapy (Subsequent Anti Cancer Therapy eCRF page).

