8.6 Interim Analysis

There are 3 interim and 1 final analyses planned:

- A planned analysis of phase 1 results at the completion of dose escalation for both combinations will be conducted.
- An analysis of the safety and efficacy results in each phase 2 arm will be conducted separately after 21 subjects in the primary efficacy population (used in the two-stage design) have had at least 2 post-baseline disease assessments.
- The final analysis by efficacy populations of all subjects in the IMO-2125 + ipilimumab arm will be done when all subjects have had at least 2 post-baseline disease assessments.

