9.2 Primary Efficacy Analyses

The primary efficacy endpoint, investigator-assessed ORR using RECIST v1.1, will be analyzed for all subjects in the PPIEE population and the first 21 patients in the PIIEE, as well as the PIIEE population and SIIIEE population combined using a one-sided, one sample exact binomial test with $\alpha = 0.025$ in each test. The proportion of subjects achieving a best confirmed response of CR or PR will be tested against the null rates of 0.11 and 0.05 for ipilimumab and pembrolizumab, respectively (Hodi et al, 2010).

The primary efficacy analyses will test the following hypotheses:

H_0 : The ORR assessed using the RECIST v1.1, for subjects in the IMO 2125 + ipilimumab treatment arm, is no larger than 0.11;

H_1 : The ORR assessed using the RECIST v1.1, for subjects in the IMO 2125 +ipilimumab treatment arm, is at least 0.35.

H_0 : The ORR assessed using the RECIST v1.1, for subjects in the IMO 2125 +pembrolizumab treatment arm, is no larger than 0.05;

H_1 : The ORR assessed using the RECIST v1.1, for subjects in the IMO 2125 +pembrolizumab treatment arm, is at least 0.35.

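### Section 8.1 limits eligible scans to those before "response", where progression was very probably meant; secondarily, the 21-subject ORR test has no stated cut-off that lets late responses be confirmed

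*SAP*

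**What the plan says.** **Which scans count.** SAP Section 8.1 opens by requiring confirmation: "The best overall response is the best response across all disease assessment visits after baseline taking into account requirements for confirmation". It sends the reader to Section 8.1.1 or 8.1.2 for the assignment rules and ends with the sentence that limits the scans: "Only visit-level disease assessments prior to the start of new anti-cancer therapy or response per the appropriate criteria will be considered".

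**What confirmation needs.** Section 8.1.1: "The minimum interval for confirmation of CR and PR is 28 days". In Table 6 a confirmed CR or PR arises only from two visits, and a CR or PR with no second visit becomes SD. Section 8.5 defines ORR on the best confirmed response. Section 9.2 tests that quantity: "The proportion of subjects achieving a best confirmed response of CR or PR will be tested against the null rates of 0.11 and 0.05".

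**When the test is made.** Section 8 says the ipilimumab-arm primary analysis, "including the hypothesis test of the ORR, will be performed on the first 21 patients in the PIIIE Population". Section 8.6 places an analysis of each Phase 2 arm "after 21 subjects in the primary efficacy population (used in the two-stage design) have had at least 2 post-baseline disease assessments". It then lists one later analysis, for one arm only: "The final analysis by efficacy populations of all subjects in the IMO-2125 + ipilimumab arm will be done when" all of those subjects have had at least two post-baseline assessments.

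**Unconfirmed responses.** Section 8.1.2 labels a CR or PR seen only at the last assessment before an interim analysis as uCR or uPR. It does not say whether these count in the Section 9.2 test.

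**The concern.** (a) The confirmatory scan comes after the first CR or PR. A rule that admits only scans before response removes the scan that confirmation depends on. This is the only sentence in the plan that sets the window of eligible scans for the primary endpoint, and progression does not appear in it. The endpoint is investigator-assessed in an open-label study and is decided at 6 of 21 responders (ipilimumab arm) or 4 of 21 (pembrolizumab arm). A rule that the programmer has to reinterpret after data exist is a poor basis for it.

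(b) Phase 2 scans are scheduled at Weeks 8, 17 and 29. A subject can meet the two-assessment minimum at Week 17 with a first response at that visit and no time yet to confirm it. Counting only confirmed responses then loses a possible true responder. Counting uCR/uPR instead would let in responses that never confirm.

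**Working it through.** **Part (a): the passages side by side**

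| Place in SAP | Rule | Effect if Section 8.1 is taken literally |
|---|---|---|
| Section 8.1, first sentence | Best response, allowing for confirmation | Cannot be met |
| Section 8.1.1, Table 6 | CR/PR needs a second CR/PR at least 28 days later; no second visit gives SD | Every responder becomes SD |
| Sections 8.5 and 9.2 | ORR is confirmed CR or PR | Zero responders |

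Reading *progression* for *response* makes all three workable, so that is very probably what was meant. Two gaps remain in the text as it stands:

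- No progression limit is set, and Table 6 has no row for PD followed by CR or PR. A RECIST v1.1 response after PD is therefore not excluded. Little data of this kind should exist: treatment runs only in the absence of unequivocal progression (Section 3.2.1), and follow-up scans stop at RECIST v1.1 PD (Section 3.2.2). Some can exist, because Table 5, footnote 19, schedules confirmatory scans for progressive disease.
- The cross-reference to Section 8.1.2 leads to the rules for unconfirmed interim responses. The irRC/irRECIST confirmation rules are in Section 8.1.3.

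**Part (b): inputs**

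From SAP Section 4: 10 subjects in Stage 1 and 11 more in Stage 2, alternative rate 0.35. Ipilimumab arm: null 0.11, continue at a = 2 or more, reject at r = 6 or more. Pembrolizumab arm: null 0.05, a = 1, r = 4.

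Assumed, because the SAP gives neither: a share f of responses in the last k subjects is still unconfirmed at the test.

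**Formula**

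P(reject) = Σ over x from a to 10 of P[Bin(10, p) = x] × P[Bin(11 − k, p) + Bin(k, p(1 − f)) ≥ r − x]

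**The plan's own figures (f = 0)**

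| Arm | Power at 0.35 | Early stop under null | Expected N under null | Exact type I error |
|---|---|---|---|---|
| Ipilimumab | 0.7731 (SAP 77%) | 0.6972 (69.7%) | 13.33 (13.33) | 0.0206 |
| Pembrolizumab | 0.9592 (SAP 96%) | 0.5987 (60%) | 14.41 (14.41) | 0.0180 |

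The design calculation reproduces.

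**Only confirmed responses count (Section 9.2): power at 0.35**

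| Affected subjects | f = 10% | 20% | 30% |
|---|---|---|---|
| Ipilimumab, last 5 | 0.753 | 0.732 | 0.710 |
| Ipilimumab, all 11 in Stage 2 | 0.727 | 0.673 | 0.611 |
| Pembrolizumab, last 5 | 0.954 | 0.948 | 0.941 |
| Pembrolizumab, all 11 in Stage 2 | 0.946 | 0.928 | 0.904 |

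In the last-5 case at ORR 0.35, the expected number of responses lost is 5 × 0.35 × f = 0.18, 0.35 or 0.53. Type I error falls as well (last 5: ipilimumab 0.0186, 0.0167, 0.0149; pembrolizumab 0.0166, 0.0154, 0.0142).

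**Opposite reading, uCR/uPR counted**

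Suppose the true confirmed rate equals the null and a share g of counted responses never confirms. The counted rate is then null/(1 − g). For g = 10, 20, 30%:

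- Ipilimumab: 0.11/(1 − g) = 0.122, 0.138, 0.157; type I error 0.033, 0.054, 0.092.
- Pembrolizumab: 0.05/(1 − g) = 0.056, 0.063, 0.071; type I error 0.025, 0.037, 0.056.

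The target is 0.025 per arm. This applies g to all 21 subjects, which is generous, since Section 8.1.2 concerns only a response at the last assessment before the analysis.

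**Waiting time**

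From Week 17, the minimum interval is 28 days = 4 weeks. The scheduled Week 29 scan comes 29 − 17 = 12 weeks later.

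**The case against.** The strongest reply on (a) is that the slip is obvious. The surrounding rules show the intent, nobody would program a rule that makes every responder SD, and post-progression responses are limited by when treatment and scanning end. That stands as to consequence. A reader might infer that the plan as written gives an ORR of zero and no power; the rest of the document does not support that as what would happen. It does not excuse leaving the sentence uncorrected, because the progression limit it was presumably meant to carry is stated nowhere else in Section 8.1 or Table 6.

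On (b), a reader might infer that the plan tests ORR before responses can be confirmed. Section 8.6 does not say so. It describes the 21 subjects as those used in the two-stage design but never states that the hypothesis test is run at that analysis, and its own count makes these analyses interims. The ipilimumab arm has a later analysis at which the test could be made. The inference is firmer for pembrolizumab, where no later analysis is listed, but the loss there is small. Two assessments is also a minimum: earlier-enrolled subjects will usually have more scans, and a Week 8 responder's second assessment can itself be the confirmation. The scenario with all 11 Stage 2 subjects affected is therefore extreme.

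It is also tempting to claim inflated type I error, or to rule it out. Section 9.2 points to confirmed responses only, and then type I error falls. But Section 8.1 names Section 8.1.2 as a source of assignment rules, and Section 8.1.2 is silent on the test, so the inflating reading is not closed off.

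**Conclusion.** (a) holds. The sentence is wrong as written and contradicts the confirmation requirement in Sections 8.1, 8.1.1, 8.5 and 9.2. It is a wording correction, but to a primary-endpoint rule, and should be made before the analysis. Its practical effect is probably small, and the size of any effect from counting post-progression responses cannot be derived from the document.

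(b) is a secondary, cheap improvement, conditional on the test being run at the 21-subject analysis. On the assumed 10–30% unconfirmed share in the last 5 subjects, power falls from 77% to 75–71% (ipilimumab) and from 96% to 95–94% (pembrolizumab). If uCR/uPR were counted and 10–30% of counted responses never confirmed, type I error would be 3.3–9.2% (ipilimumab) and 2.5–5.6% (pembrolizumab), against 2.5%. Both ranges are illustrative.

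**What to change.** **(a)**
- In Section 8.1, count assessments before new anti-cancer therapy and up to and including progression by the applicable criteria: first PD for RECIST v1.1, confirmed PD for irRC and irRECIST.
- Add a row to Table 6 making PD followed by CR or PR a best response of PD.
- Correct the cross-reference from Section 8.1.2 to Section 8.1.3.

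**(b)**
- In Section 8.6, state that each arm's ORR test is run at a fixed cut-off: when each of the 21 subjects has completed the Week 17 assessment (or can no longer have it), and any CR or PR first documented by then has had its scan at least 28 days later or can no longer be confirmed. A first response appearing later, at Week 29 or in three-monthly follow-up, must not move the cut-off; otherwise the wait has no end.
- In Section 8.1.2, state that uCR and uPR are displayed only and do not count in the Section 9.2 test.

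**Cost.** SAP wording for both parts. Part (b) adds a wait for the last-enrolled subjects of about 4 weeks, or up to about 12 if the Week 29 scan serves as confirmation. No new scans are needed, since confirmatory scans are already in the schedule.

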8.1.1 Confirmed Response using RECIST v1.1

Table 6 shows how the investigator-assessed Best Overall Confirmed Response is assigned for each subject. The table is based on the Best Overall Response confirmation table in the RECIST v1.1 guidelines (Appendix C).

Table 6: Confirmed Response using RECIST V1.1

Visit-Level Response	Next Visit Level Response	Confirmed Response
CR	CR	CR (if visit-level disease assessments are \geq 28 days apart), otherwise SD
CR	PR	PR (if visit-level disease assessments are \geq 28 days apart); otherwise SD
CR	SD	SD
CR, PR, SD	PD	SD
CR, PR	NE	SD
PR	CR, PR	PR (if visit-level disease assessments are \geq 28 days apart); otherwise, SD
PR	SD	SD
SD	SD, CR, PR, PD, NE	SD
PD	PD	PD
NE	NE	NE
CR, PR, SD	No 2 nd visit	SD
PD	No 2 nd visit	PD
NE	No 2 nd visit	NE

CR = complete response, PR = partial response, SD = stable disease, PD = progressive disease,
NE = not evaluable.

The minimum interval for confirmation of CR and PR is 28 days. Subjects must have at least one post-baseline disease assessment to be assigned SD as the best overall response; otherwise, there is no minimum interval for assignment of SD as the best overall response. Because scans of target and non-target lesions can be done on different dates, time between disease assessments is determined using the following algorithm: (1) calculate the time in days between initial and confirmatory scans for all target and non-target lesions separately (confirmatory assessment date - initial assessment date +1); (2) select the minimum time; and (3) compare to 28 days to determine if the confirmation criterion were met. Date of confirmed best overall response is determined using scan dates as follows: if BOR is CR or PR response date is the latest date of target or non-target lesion scan date or else use the assessment date.

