Disease sites must be assessed using the same technique as baseline, including consistent administration of contrast and timing of scanning. If a change needs to be made the case must be discussed with the radiologist to determine if substitution is possible. If not, subsequent objective statuses are indeterminate.

1. Target Disease

- Complete Response (CR): Complete disappearance of all target lesions with the exception of nodal disease. All target nodes must decrease to normal size (short axis <10 mm). All target lesions must be assessed.
- Partial Response (PR): Greater than or equal to 30% decrease under baseline of the sum of diameters of all target measurable lesions. The short diameter is used in the sum for target nodes, while the longest diameter is used in the sum for all other target lesions. All target lesions must be assessed.
- Stable: Does not qualify for CR, PR or Progression. All target lesions must be assessed. Stable can follow PR only in the rare case that the sum increases by less than 20% from the nadir, but enough that a previously documented 30% decrease no longer holds.
- Objective Progression (PD): 20% increase in the sum of diameters of target measurable lesions above the smallest sum observed (over baseline if no decrease in the sum is observed during therapy), with a minimum absolute increase of 5 mm.
- Indeterminate. Progression has not been documented, and
 - one or more target measurable lesions have not been assessed;
 - or assessment methods used were inconsistent with those used at baseline;
 - or one or more target lesions cannot be measured accurately (eg, poorly visible unless due to being too small to measure);
 - or one or more target lesions were excised or irradiated and have not reappeared or increased.

2. Non-target Disease

- CR: Disappearance of all non-target lesions and normalization of tumor marker levels. All lymph nodes must be 'normal' in size (<10 mm short axis).
- Non-CR/Non-PD: Persistence of any non-target lesions and/or tumor marker level above the normal limits.

- PD: Unequivocal progression of pre-existing lesions. Generally the overall tumor burden must increase sufficiently to merit discontinuation of therapy. In the presence of SD or PR in target disease, progression due to unequivocal increase in non-target disease should be rare.

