Appendix Table 4 Best overall response when confirmation of CR and PR required.

Overall response First time point	Overall response Subsequent time point	BEST overall response
CR	CR	CR
CR	PR	SD, PD or PR ^a
CR	SD	SD provided minimum criteria for SD duration met, otherwise, PD
CR	PD	SD provided minimum criteria for SD duration met, otherwise, PD
CR	NE	SD provided minimum criteria for SD duration met, otherwise NE
PR	CR	PR
PR	PR	PR
PR	SD	SD
PR	PD	SD provided minimum criteria for SD duration met, otherwise, PD
PR	NE	SD provided minimum criteria for SD duration met, otherwise NE
NE	NE	NE

CR = complete response, PR = partial response, SD = stable disease, PD = progressive disease, and NE = inevaluable.

a If a CR is truly met at first time point, then any disease seen at a subsequent time point, even disease meeting PR criteria relative to baseline, makes the disease PD at that point (since disease must have reappeared after CR). Best response would depend on whether minimum duration for SD was met. However, sometimes 'CR' may be claimed when subsequent scans suggest small lesions were likely still present and in fact the patient had PR, not CR at the first time point. Under these circumstances, the original CR should be changed to PR and the best response is PR.

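### Table 6 scores CR followed by PR at least 28 days later as a confirmed PR and omits the condition in the RECIST table it cites, so a recurrence after a true CR can count as a response in the primary ORR

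*SAP*

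**What the plan says.** Section 8.1 derives best overall response by program from the recorded visits: it is "determined by examining investigator-assessed visit-level responses and determining the best confirmed response using the assignment rules" of Section 8.1.1, that is, Table 6. For CR followed by PR, Table 6 returns "PR (if visit-level disease assessments are \geq 28 days apart); otherwise SD". Its stated source is the confirmation table in Appendix C: "The table is based on the Best Overall Response confirmation table in the RECIST v1.1 guidelines (Appendix C").

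That source is Appendix Table 4. For CR followed by PR it lists three possible outcomes, SD, PD or PR, and footnote a decides between them:

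- If the CR was real, "any disease seen at a subsequent time point, even disease meeting PR criteria relative to baseline, makes the disease PD at that point". Best response then depends on whether the minimum SD duration was met.
- If the CR was claimed but small lesions were probably still present: "Under these circumstances, the original CR should be changed to PR and the best response is PR".

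The result feeds the primary endpoint in Section 9.2: "The proportion of subjects achieving a best confirmed response of CR or PR will be tested against the null rates of 0.11 and 0.05" for the ipilimumab and pembrolizumab arms respectively.

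**The concern.** Table 6 keeps one of the three outcomes in its source and replaces the clinical condition (was the first CR real?) with an interval condition (28 days). The two tables can therefore classify the same pair of recorded visits differently: non-responder under Appendix Table 4, responder under Table 6. Relative to the source table, the omission can only add responders. It matters because the primary test is a one-sided exact binomial test on about 21 subjects per arm, where a single subject can settle the result. If such a subject appears, the classification would have to be argued after the data are known, with each side able to cite the SAP.

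**Working it through.** **1. The two rules side by side, for a recorded CR followed by a recorded PR**

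| Situation | Appendix Table 4, footnote a | Table 6 (28 days or more apart) |
|---|---|---|
| CR called in error, revised to PR | PR, responder | PR, responder |
| CR real, disease seen at the next visit | PD at that visit; best response SD or PD, non-responder | PR, responder |

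The rows agree in the first situation and conflict in the second.

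**2. Does the 28-day condition screen out the conflict?** Hardly. Scheduled scans are at Weeks 8, 17 and 29, each within 7 days (Table 5 notes). The shortest scheduled gap is 9 weeks less two 7-day windows: 63 - 14 = 49 days. Confirmatory scans are to be done at least 4 weeks after first documentation. Only an unusually early repeat scan would fall to SD.

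**3. Can a recurrence be recorded as PR without a coding error?** Yes, in two ways under Appendix C.

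- *Non-target disease.* Appendix Table 2 maps target CR with non-target Non-CR/Non-PD and no new lesion to PR. A non-target lesion that reappears without unequivocal progression fits that row.
- *Nodal regrowth.* Target PD needs a "20% increase in the sum of diameters of target measurable lesions above the smallest sum observed" and also an absolute increase of at least 5 mm. A node below 10 mm is normal, but its actual size stays in the sum. Illustration: one target node of 20 mm at baseline, 9 mm at CR, then 11 mm. The change from nadir is +2 mm, or 2/9 = 22%, so the 5 mm minimum is not met and the visit is not PD. At 11 mm the node is no longer normal, so the visit is not CR. The fall from baseline is 9/20 = 45%, which meets PR.

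**4. The design figures in Section 4.** Continue if x1 >= r1 of 10; reject if the total is >= r of 21. With b the binomial probability:

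- Early stop = sum of b(10, x, p0) over x < r1
- Expected N = 10 + 11 × (1 - early stop)
- Rejection probability = sum over x >= r1 of b(10, x, p) × P(Bin(11, p) >= r - x)

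Ipilimumab (r1 = 2, r = 6, p0 = 0.11, p1 = 0.35): early stop 0.3118 + 0.3854 = 0.6972; expected N 10 + 11 × 0.3028 = 13.33; power 0.7731; type I error 0.0206. The SAP states 69.7%, 13.33 and 77%.

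Pembrolizumab (r1 = 1, r = 4, p0 = 0.05, p1 = 0.35): early stop 0.95^10 = 0.5987; expected N 10 + 11 × 0.4013 = 14.41; power 0.9592; type I error 0.0180. The SAP states 60%, 14.41 and 96%.

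All stated figures reproduce.

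**5. What one reclassified subject does at the boundary.** Exact one-sided p-value P(X >= k | 21, p0), against 0.025:

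| Arm | At the cut-off | One fewer |
|---|---|---|
| Ipilimumab, p0 = 0.11 | 6/21: 0.0223 | 5/21: 0.0731 |
| Pembrolizumab, p0 = 0.05 | 4/21: 0.0189 | 3/21: 0.0849 |

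**6. Range under an assumption.** The SAP gives no frequency for this sequence. If it raised the apparent null response rate by 1, 2 or 3 percentage points, the type I error of the two-stage rule would go from 0.0206 to 0.0303, 0.0427 or 0.0581 (ipilimumab) and from 0.0180 to 0.0325, 0.0525 or 0.0782 (pembrolizumab). These increments are assumed, not estimated.

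**The case against.** The strongest reply is that footnote a acts before Table 6. An investigator who follows Appendix C records a relapse after CR as PD, and Table 6 sends CR then PD to SD, a non-responder. From a zero nadir, target regrowth of 5 mm or more already meets target PD, and a new unequivocal lesion is PD. On this view a CR-then-PR pair reaches Table 6 only when nobody judged it a relapse. Part of this stands: many true relapses will be recorded as PD and handled correctly. It does not remove the conflict. Appendix Table 4 itself takes CR then PR as its input and still does not return PR automatically, and step 3 of the working shows recurrences that the visit rules code as PR.

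A second reply is that a table based on another need not copy it. That is true, and Section 8.1.1 openly waives the minimum interval for SD. It neither states nor justifies this departure.

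Four stronger readings are tempting but not supported:

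- *Table 6 always gives PR, and the source always gives PD.* Table 6 gives SD below 28 days, and Appendix Table 4 allows PR when the CR was wrong.
- *Best response and PFS/DoR already contradict each other.* Under Section 8.5 a recorded PR is a valid assessment without progression, so both use PR; if PD is recorded, both use PD. They diverge only if the visit is recoded for one and not the other.
- *Table 7 has the same defect.* It has the same row but cites Appendices B and D, which do not contain footnote a.
- *Every unrevised CR-then-PR pair is a progression.* Appendix Table 2 also gives PR when target disease is in CR and a non-target site is indeterminate or missing. No disease has then been seen, and the footnote's PD branch does not apply.

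**Conclusion.** The point holds as a conflict between Table 6 and the table it names as its source, in a category that feeds the primary ORR. The exposure is narrow. It needs a CR that stands, disease at the next visit recorded as PR rather than PD, an interval of at least 28 days, and no confirmed response from an earlier pair of visits. The documents do not allow its frequency to be estimated, and it is probably rare.

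A reader might infer from the p-values that the ORR is materially inflated. They do not show that: any single reclassified subject at the cut-off has the same effect. They show only that neither test has room for one wrong responder. The design figures in Section 4 are correct and unaffected. The rule should be corrected because doing so is cheap and the omission, relative to the cited criteria, can only favour response.

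**What to change.** Amend the CR-then-PR row of Table 6 only, and query every such pair before database lock:

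- If the investigator revises the first CR to PR, score PR, provided the assessments are at least 28 days apart.
- If the CR stands and disease is seen at the second visit, treat that visit as PD. The existing CR-then-PD row then gives SD (non-responder), and PFS and DoR use the same date.
- If the PR arises only from a missing or indeterminate non-target assessment with no disease seen, do not treat it as progression.

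The cost is one table row, a sentence pointing to footnote a, and a few data queries. The sample size, cut-offs and test are unchanged. The ORR can only stay the same or become slightly less favourable.
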